5.3. Timeline Week 38 Final Analysis

- | | |
|----------------------------------------------------------------|------------------|
| • Estimated Last patient completing 6-month extension Period 2 | 14 November 2022 |
| • Estimated Database Lock | 14 December 2022 |
| • Estimated Release of study Tables and Listings | 31 January 2023 |

6. GENERAL CONSIDERATIONS FOR DATA ANALYSES AND DATA HANDLING

Descriptive statistics for continuous variables include n, mean, standard deviation, standard error, median, minimum, and maximum. Descriptive statistics for categorical variables include patient counts and percentages.

6.1. Day 1

Day 1 is the date of first dose of treatment with study drug.

6.1.1. Study Day

Study days will be numbered relative to the first day of study drug administration.

- Study days will be numbered relative to study start (i.e., ..., -2, -1, 1, 2, ...; with Day 1 being the start of study drug and Day -1 being the day before the start of study drug).
- The elapsed time since Day 1 for an event (e.g. onset of an adverse event) will be calculated as [date of event – date of Day 1 + 1].
- For the purpose of converting days to years or months, one year = 365.25 days, and one month = 30.44 days.

6.1.2. Baseline Value

Baseline is the last observed non-missing data prior to the first dose of study drug. Per the protocol, this should be the assessment on Day 1 before the first study drug dose with the exception of medical history, demographics, physical and neurological examinations, ECGs, and labs, which are assessed at the screening visit.

6.1.3. Enrollment Date

The date the patient was enrolled into the study (the baseline visit date).

6.1.4. End of Treatment Value

End of treatment value is the last non-missing post-baseline value for each patient.

6.2. Variable Definitions

6.2.1. Age

Patient age will be calculated as the integer part of the number of years from date of birth to the date of signing the informed consent form, using the following formula:

$$\text{Age} = \text{integer part of } (\text{date of informed consent} - \text{date of birth} + 1) / 365.25$$

6.2.2. Body Mass Index

Body mass index (BMI) will be calculated as follows:

$$\text{BMI (kg/m}^2\text{)} = [\text{weight (kg)}] / [\text{height (m)}]^2$$

6.2.3. Prior and Concomitant Medication

A prior medication is defined as any non-study medication that started before the date of first dose of study drug.

Concomitant medication is defined as any non-study medication that:

- Started before the date of first dose of study drug and is ongoing throughout the study or ends on/after the date of first study medication administration.
- Started on/after the date of first dose of study drug and is ongoing or ends during the course of study medication.

The start/stop dates recorded in the CRF will be used to determine medication prior to or during the study. A medication can be considered both prior and concomitant if it was started prior to the first dose of study drug and continues to be taken after the first dose of study medication. Unresolved missing start dates will be handled as follows for determination of concomitance:

- Partial dates will be imputed in such a way as to consider the non-study medication as prior and/or concomitant if it is possible that the missing information could lead to a prior and/or concomitant outcome.

6.2.4. Treatment Emergent Adverse Events (TEAEs)

Treatment emergent adverse events (denoted as TEAE hereafter) are defined as adverse events with onset dates on or after the start of study drug.

All reports of adverse events should include the severity and relationship to study drug that are determined by the investigators. In the event of missing information, the following rules will be applied for the adverse event summaries:

- AEs with missing onset dates will be included as treatment- emergent (unless end date is prior to the first dose date)
- AEs with missing severity will be counted as severe in severity
- AEs with missing relationship to study drug will be counted as related

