11.2. Adverse and Serious Adverse Events

Throughout the study, the Investigator will monitor each patient for evidence of drug intolerance and for the development of clinical and/or laboratory evidence of an AE. An AE assessment will be made by the investigator on a routine basis throughout treatment and at each post-treatment evaluation. In order to standardize the approach to assessing the occurrence of AEs, the investigator should make a judgment as to any change in condition or AEs that were not present before study drug administration when he obtains the parent/patient's response to how they are feeling. Patients having TEAEs will be followed until they return to normal or become stabilized.

All TEAEs that occur during the course of the study must be reported in detail on the appropriate CRFs, patient's source document record, and on any other report form required by National Law. All efforts will be made to follow-up adverse events until resolution.

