11.2.1. Definition of Adverse Events

11.2.1.1. Adverse Event

An AE is an undesirable medical occurrence (sign, symptom, or diagnosis) or worsening of a pre-existing medical condition (e.g., diabetes, congestive heart failure, rheumatoid arthritis, psoriasis) that occurs at any time after signing of the ICF whether or not it is considered to be related to treatment. Worsening of an existing medical condition is when a condition present at the time of signing of the ICF (e.g., cancer, diabetes, gout) becomes more severe, more frequent, or increased in duration during the study. Hospitalizations for pretreatment conditions (e.g., elective cosmetic procedures) or surgeries that were planned before entry into the study are not considered AEs.

The Investigator is responsible for reviewing laboratory test results and determining whether an abnormal value represents for the patient a change from the time of signing of the ICF. In general, abnormal laboratory findings without clinical significance (based on the Investigator's judgment) should not be recorded as AEs. Clinically significant changes occurring after the signing of the ICF are considered AEs; however, the reported adverse event should include the underlying diagnosis or resulting clinical sequelae. Patients having clinically significant AEs will be followed until they return to normal or become stabilized.

Throughout the study, the Investigator will monitor each patient for evidence of drug intolerance and for the development of clinical and/or laboratory evidence of an adverse event. An AE assessment will be made by the Investigator on a routine basis throughout the study. All AEs which occur during the course of the study must be reported in detail on the appropriate CRF

page and on any other report form required by national law. All TEAEs must be followed to a satisfactory resolution.

All AEs will be collected from study Screening until the patient is discharged from the study.

Application site irritation scores of 1, 2, or 3 should not be recorded as AEs but will be assessed and recorded as part of the skin irritation score examinations. Skin irritation recorded with a score of '4' (as assessed by the Investigator) will be recorded as part of the skin irritation examination, and will also be recorded by the Investigator as an AE. The Investigator should report as an expedited AE (within 24 hours of assessment) to the Sponsor.

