5.2. Data included in Period 1 Analyses

The records to be included in the Period 1 analyses will include all records with a nominal visit of ≤ 4 (Week 14/ET). All summaries will include one column only identified as ZYN002.

In an attempt to include all Period 1 Concomitant Medications and Adverse Events in the Period 1 analyses TGG will need to calculate a Week 14 Date for both subjects who completed Period 1 and who discontinued in Period 1 before Week 14. This will be accomplished by the following steps using the last non-missing value as the actual or imputed Week 14 date:

- a) If a subject completes Period 1 then use their actual Week 14 Date.
- b) If a subject discontinues before Week 14 date and their last nominal visit is identified as Week 14/ET then add ‘X’ days to that date to get to Day 98 (7 times 14).
- c) If Week 6, TGG will impute the Week 14 cutoff date to be the Week 6 date plus (7 times 8) to get the Week 14 imputed Date

d) If Day 1, TGG will impute the Week 14 date to be Day 1 plus (7 times 14)

Treatment emergent adverse events and concomitant medication summaries will include start dates that occur any time before treatment begins and treatment ends. Refer to [Section 6.2.3](#).

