8.1.1. Adverse Events

All adverse events will be coded using the Medical Dictionary for Regulatory Activities (MedDRA) Version 21.0 or greater. Treatment emergent adverse events (TEAEs) are defined as adverse events with onset dates on or after the first dose of study drug.

All AE summaries will include total number of TEAEs and total number of patients with AEs.

An overall summary of adverse events will include number (%) of patients reporting ≥ 1 TEAE (and number of TEAEs), TEAE by Severity (and number of TEAEs), treatment-related TEAEs (and number of TEAEs), SAEs (and number of TEAEs), TEAE by outcome (and number of TEAEs), TEAEs that resulted in treatment discontinuation (and number of TEAEs). In addition, the total number of TEAEs by subject will be summarized.

Additionally, summaries will be presented for all TEAEs by system organ class and preferred term (overall and by severity). TEAEs determined by the investigator to be treatment-related (overall and by severity). Serious AEs will also be summarized. Adverse events causing permanent discontinuation from treatment will be summarized, fatal adverse events will be summarized, and TEAEs by preferred term in descending order will be summarized.

The incidence of adverse events will be summarized using descriptive statistics by system organ class and preferred term. Patients are counted only once in each system organ class category, and only once in each preferred term category. Treatment-related adverse event summaries will include adverse events with missing relationship to study drug. For the summaries by severity, patients and TEAEs are counted at the greatest severity.

AEs will be summarized separately for each treatment Period (1, 2) and overall (the whole study).

Listings for fatal AEs, serious AEs, and AEs leading to discontinuation, will also be presented.

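### The TEAE definition has no worsening clause, so an AE that begins between consent and Day 1 and worsens on ZYN002 can be left out of the TEAE tables

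*SAP*

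**What the plan says.** - **SAP 6.2.4 and 8.1.1.** Both classify by onset date. In 6.2.4, TEAEs "are defined as adverse events with onset dates on or after the start of study drug". Section 8.1.1 has TEAEs as "defined as adverse events with onset dates on or after the first dose of study drug". Section 6.2.4 adds defaults for incomplete records: an AE with no onset date counts as treatment-emergent unless it ended before first dose, missing severity is taken as severe, and missing relationship as related. Neither section mentions an earlier event that gets worse.
- **Protocol 11.2.1.1.** "All AEs will be collected from study Screening until the patient is discharged from the study". The opening sentence of the AE definition includes the worsening of a pre-existing condition at any time after consent. The section then explains the term: "Worsening of an existing medical condition is when a condition present at the time of signing of the ICF", and that condition later increases in severity, frequency or length.
- **Protocol 11.2.** The investigator is to judge "any change in condition or AEs that were not present before study drug administration".
- **Protocol 11.4.** Each AE carries an onset date, a resolution date and an intensity. There is no instruction to open a new record, or to re-date the existing one, when intensity rises.
- **SAP 5.2.** For Period 1, the TEAE and concomitant medication summaries "will include start dates that occur any time before treatment begins and treatment ends".

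**The concern.** The Screening Visit falls on Days -28 to -8 (Protocol Table 4), so the database can hold AEs that began before any drug was applied. If one of these is still ongoing at Day 1 and then deteriorates on treatment, that deterioration is on-treatment safety information. Under an onset-only rule, a single record dated before first dose fails the test however much it worsens.

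The result depends on an accident of timing. A condition already present at consent that worsens after dosing becomes an AE by virtue of the worsening, so its natural onset date is on treatment and it counts. The same condition starting a few days after consent is already an AE with a pre-dose onset, and no rule moves that date. For events of this kind the omission can only lower the TEAE counts. Safety and tolerability are the primary objective, and TEAE incidence, severity and relatedness are its main tabulated readout.

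**Working it through.** The documents give no figure on this point, so there is none to reproduce. The check has two parts: applying the rule to test records, and putting a scale on the gap.

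**1. The rule in SAP 6.2.4 applied to test records (Day 1 = first dose)**

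| Record | TEAE under 6.2.4? |
|---|---|
| One record, onset Day -5, worsens on Day 20 | No |
| Worsening entered as a separate AE, onset Day 20 | Yes |
| Onset date missing, no end date before first dose | Yes |

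The first two rows are the same clinical course. Only the way the site enters it differs, and neither document settles that.

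**2. Scale**

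Inputs from the documents:
- About 20 patients (Protocol 7.2).
- Screening Visit 8 to 28 days before first dose (Protocol Table 4).
- An event rate borrowed from the sponsor's earlier open-label Fragile X study (Protocol 5.3.2): 20 enrolled, 33 TEAEs in 12 weeks, 25 of them judged unrelated.

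Assumptions, not in the documents:
- The borrowed rate applies to the screening period of this trial, with every patient in that study contributing the full 84 days.
- Between 5% and 20% of screening-period AEs worsen on drug.

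Arithmetic:
- Rate = 33 / (20 × 84) = 33 / 1,680 = 0.0196 AEs per patient-day.
- Pre-dose patient-days: 20 × 8 = 160 to 20 × 28 = 560.
- Expected pre-dose AEs: 160 × 0.0196 = 3.1 to 560 × 0.0196 = 11.0.
- Events affected: 0.05 × 3.1 = 0.2 to 0.20 × 11.0 = 2.2.
- Using only the 25 unrelated events, 25 / 1,680 = 0.0149 per patient-day. This gives 2.4 to 8.3 pre-dose AEs, and 0.05 × 2.4 = 0.1 to 0.20 × 8.3 = 1.7 affected.

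**3. What one patient does to a table**

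1/20 = 5 percentage points. For a given preferred term, 0/20 (exact 95% CI 0 to 16.8%) becomes 1/20 (0.1% to 24.9%).

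**4. SAP 5.2 against SAP 6.2.4**

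Read literally, 5.2 admits start dates before treatment into the Period 1 TEAE summaries, and 6.2.4 excludes them. The 5.2 sentence is probably a slip for a phrase meaning between the start and end of treatment, and its cross-reference is to 6.2.3, the medication section. On the literal reading it would admit every pre-dose AE, worsened or not. Neither sentence picks out pre-dose events that worsen on drug.

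**The case against.** A reader might infer that every such event is missing from every TEAE table. The documents do not go that far. The opening sentence of Protocol 11.2.1.1 counts worsening of a pre-existing condition without requiring that it predate consent, and Protocol 11.2 takes study drug, not consent, as its reference point. A site could reasonably enter the worsening as a new AE with an on-treatment date, and 6.2.4 would then capture it. The onset rule is also not absolute, since AEs with missing onset dates count, and SAP 5.2 read literally points the other way for Period 1. All of this stands. It leaves the outcome to each site's habit, because no sentence tells a site to split or re-date a record. The seizure instruction in the protocol's Safety Monitoring text, under which any increase in frequency or severity is recorded as an AE, shows that the authors wrote an explicit rule where they wanted one.

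A reader might also infer that the event is lost, or that 3 to 11 events are at stake. Neither is supported. Listing 16.18.1 covers AEs in enrolled patients without a TEAE restriction. The serious, fatal and discontinuation tables are titled as adverse events, not TEAEs, and may show it. Shift tables cover ECG, examination and laboratory changes. The 3 to 11 figure counts all screening-period onsets. Those that resolve before Day 1 are irrelevant, and the commonest events in the source study were infections that resolved.

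The gap is also narrow. Worsening of conditions present at consent and increases in seizures are already covered, and reactions to the gel cannot predate it. What remains is a new event that starts in the screening window, is ongoing at Day 1, worsens, and stays as one record.

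**Conclusion.** The point holds in limited form. By its stated rule, the SAP leaves a single-record AE with onset between consent and Day 1 out of the TEAE incidence, severity and relatedness tables even if it worsens on ZYN002, and no passage says how such worsening is to be recorded. This is a rule that can give the wrong classification. It is not proof that events will be omitted, because that depends on how sites enter them.

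The expected effect is small: about 0.2 to 2.2 events in the whole trial. That range rests on an event rate from a different population and on an assumed share that worsens. The rate would be a little higher if patient-days were reduced for the two of 20 patients in the source study who did not complete. The correction is still worth making, because one patient in 20 is visible in any table and the omission runs in one direction.

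**What to change.** - **SAP 6.2.4 and 8.1.1.** Define a TEAE as an AE with onset on or after first dose, or with onset before first dose that worsens in severity, frequency or seriousness on or after first dose. Keep the missing-onset default.
- **Count each worsening once.** If the site enters the worsening as a separate AE dated at the worsening, count that record and not the original pre-dose record. Without this sentence both records would qualify, and the number of TEAEs reported under 8.1.1 would be inflated.
- **SAP 5.2.** Reword the sentence on start dates so that it agrees with the new definition, and correct its cross-reference.

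The cost is a few sentences in the SAP. Applying the clause to a single record also requires the fact and date of worsening to be recorded. The protocol's list of AE data items does not include them, so a short CRF completion note may be needed. The TEAE count may rise slightly.

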6.3. General Summary Table and Individual Subject Data Listing Considerations

All population summaries will be summarized on the safety analysis set unless otherwise noted.

6.3.1. Patient Disposition

The number of patients enrolled, patients in the safety analysis set, patients in the Modified intent-to-treat set, patients in the Pharmacokinetic set, patients who completed the study, and patients who discontinued the study, will be summarized using descriptive statistics. (Table 14.1.1).

Reasons for study discontinuation will also be summarized for patients who discontinued the study. The number of patients who entered the 6-month extension period will also be summarized. This summary will include the set of enrolled patients.

6.3.2. Demographics

The continuous variables of patient age, weight (kg), height (cm), and BMI (kg/m²) will be summarized using descriptive statistics. The categorical variables of patient sex, ethnicity, and race will be summarized using descriptive statistics for each category (Table 14.1.2). Missing categories will be presented if necessary.

6.3.3. Baseline Characteristics

Diagnosis, etiology, time since diagnosis (informed consent date-date of diagnosis+1/365.25), ADOS, epilepsy diagnosis, female reproductive status, urine pregnancy test results for female patients of childbearing potential will be summarized (Table 14.1.3) using descriptive statistics.

6.3.4. Medical History

Medical history will be coded using the Medical Dictionary for Regulatory Activities (MedDRA) Version 21.0 or greater. Patients with a medical history assessment, patients with at least one finding, and findings for each category will be summarized using descriptive statistics by system organ class, and preferred term (Table 14.1.4).

6.3.5. Prior Medications

All prior medications will be coded using the World Health Organization dictionary of medical codes (WHO Drug). The incidence of prior medications will be summarized using descriptive statistics by therapeutic class and preferred term (Table 14.1.5). Patients are counted only once in each therapeutic class category, and only once in each preferred term category. Prior medications will include all medications taken on or before the first dose date of study drug treatment.

6.3.6. Electrocardiogram

Electrocardiogram findings (normal, abnormal not clinically significant, abnormal clinically significant, and missing) at baseline will be summarized (Table 14.1.6) using descriptive statistics.

6.3.7. Physical Examination/Neurological Examination

Physical/Neurological examination findings for each body system will be summarized at baseline (Tables 14.1.7, 14.1.8) using descriptive statistics.

6.4. Analysis Populations

6.4.1. Safety Analysis Set

All patients who receive at least one dose of study drug will be included in the safety population. Safety population will be used for all safety evaluations.

6.4.2. Modified Intent-to-Treat (mITT)

Safety patients who have at least one post baseline (PBL) efficacy assessment will be included in the modified Intent-to-Treat population. mITT will be used for all efficacy assessments.

6.5. Pharmacokinetic Population

The PK population will consist of all patients who received at least one application of study drug and had a plasma concentration obtained from at least one post baseline assessment.

6.6. Efficacy Analysis

All efficacy analyses will be on the mITT Analysis Set.

Descriptive statistics (mean, median, standard deviation, minimum, and maximum) for continuous data and number (n) and percentage (%) for categorical data will be presented for all efficacy and safety parameters.

Baseline will be defined as the last assessment prior to the first dose of ZYN002.

6.7. Exploratory Efficacy Analysis

This study is the first study of ZYN002 in 22q patients. As such, a primary efficacy endpoint was not selected. The primary *objective* is to analyze for safety and tolerability along with determining the most clinically meaningful efficacy data resulting from this study.

The first step will be to analyze change from baseline to the end of the 14-week treatment period (Period 1). The results of the change from baseline will guide the additional types of exploratory analysis to be completed.

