6. TRIAL OBJECTIVES AND PURPOSE

6.1. Primary Objective

Primary:

To evaluate the safety and tolerability of ZYN002 administered as a transdermal gel formulation, for up to 38weeks, in patients ages 4 to < 18 years, in the treatment of symptoms of 22q.11.2 Deletion Syndrome (22qDS).

Secondary:

- To evaluate the efficacy of ZYN002 in the treatment of symptoms of 22qDS.
- To evaluate CBD and THC plasma level exposure.

Exploratory:

The identification of plasma levels of CBD metabolite(s) may be conducted.

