6.7.1. Aberrant Behavior Checklist-Community (ABC-C)

The ABC-C instrument is a scale for rating inappropriate and maladaptive behavior of people with developmental disabilities, including intellectual disability and autism spectrum disorder (ASD), (Aman & Singh, 2017). Change and percent change from Baseline to Weeks 6, 14, 22, 30 and 38/ET in the ABC-C subscales of Irritability, Social Withdrawal, Stereotypic Behavior, Hyperactivity Noncompliance, and Inappropriate Speech will be calculated. In addition, a t-test will be used to test if within treatment changes from baseline are different from 0. Responder analyses (25% and 35% improvement) from baseline to each visit in each subscale will be calculated.

The Aberrant Behavior Checklist - Community, 2nd Edition, is completed at Screening, Visit 2, Visit 3, Visit 4, Visit 5, Visit 6, and Visit 7 EOS/ET. The ABC-C asks responders to rate behaviors from “0 - not at all a problem” to “3 - the problem is severe in degree” across 58 questions. ABC consists of five subscales as follows:

Table 6: ABC-C Subscale Scoring

Subscale Number	Subscale Name	Total Score for Response to Questions	Range
I	Irritability	2, 4, 8, 10, 14, 19, 25, 29, 34, 36, 41, 47, 50, 52, 57	0 to 45
II	Social Withdrawal	3, 5, 12, 16, 20, 23, 26, 30, 32, 37, 40, 42, 43, 53, 55, 58	0 to 48
III	Stereotypic Behavior	6, 11, 17, 27, 35, 45, 49	0 to 21
IV	Hyperactivity Noncompliance	1, 7, 13, 15, 18, 21, 24, 28, 31, 38, 39, 44, 48, 51, 54, 56	0 to 48
V	Inappropriate Speech	9, 22, 33, 46	0 to 12

Additionally, the ABC-C irritability subscale was used as criteria in order for patients to be eligible to participate in Period 2. Patients had to have a >35% irritability improvement in change from baseline to end of Period 1, in order to participate in the 6-month extension (Period 2).

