10. CHANGES FROM THE PROTOCOL

None identified.

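### SAP 6.7 makes an after-the-fact choice of efficacy result part of the primary objective, alongside 30 unadjusted t-tests that the protocol did not plan

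*SAP*

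**What the plan says.** Protocol 6.1 has one primary objective: "To evaluate the safety and tolerability of ZYN002 administered as a transdermal gel formulation". Efficacy is secondary. SAP 3.1 and 3.2 repeat that split.

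SAP 6.7 departs from it. It states that "a primary efficacy endpoint was not selected", then describes the primary objective as safety and tolerability "along with determining the most clinically meaningful efficacy data resulting from this study". The first step is the change from baseline to the end of Period 1 (Week 14). After that, "The results of the change from baseline will guide the additional types of exploratory analysis to be completed".

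For the five ABC-C subscales, SAP 6.7.1 plans change and percent change at Weeks 6, 14, 22, 30 and 38/ET and says: "In addition, a t-test will be used to test if within treatment changes from baseline are different from 0". SAP 6.7.2 plans the same test for CGI-S at the same visits. ADAMS and PARS-R have change tables in SAP 11 but no stated test. No significance level, sidedness or multiplicity adjustment is given.

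Protocol 13.3 and 13.5 plan descriptive statistics only for efficacy. SAP 10, on changes from the protocol, reads "None identified".

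**The concern.** The efficacy result is to be identified from the observed data. The SAP does not say what counts as clinically meaningful or what pattern of results would mean that no effect was seen. With several scores and visits tested and no adjustment, some p-values below 0.05 are expected by chance. A score brought forward because its change looked large will have an inflated estimate.

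This bears on a stated objective. Efficacy is secondary in both documents, and SAP 4.2.1 says that 20 patients suffice for a reliable answer to the study objectives. A score chosen after the results are seen cannot give that, and a later trial sized on its unadjusted effect would be too small.

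**Working it through.** **Plan's own figure.** There is none to reproduce. SAP 4.2.1 gives 20 patients with no formal calculation, and no alpha, power, effect size or SD is stated.

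**Inputs.**
- Tests: 5 ABC-C subscales × 5 visits = 25 (SAP 6.7.1), plus CGI-S × 5 visits = 5 (SAP 6.7.2), total 30. Of these, 6 are at Week 14, 12 in Period 1 (Weeks 6 and 14) and 18 in Period 2. Only change is counted, not percent change.
- n = 20 (SAP 4.2.1).
- Assumed: two-sided 0.05 per test, no true change, correlation between scores 0–0.7 and between visits 0.3–0.85.

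**Chance of at least one p<0.05.** For k independent tests it is 1 − 0.95^k, or 1 − 0.975^k counting improvement only. The correlated case was simulated with one-sample t-tests and all 20 patients at every visit.

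| Tests | Independent, exact | Simulated | Improvement only |
|---|---|---|---|
| Week 14 (6) | 26.5% | 16–27% | 8–14% |
| Period 1 (12) | 46.0% | 24–45% | 12–26% |
| All 30 | 78.5% | 35–76% | 17–53% |

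Improvement-only figures are about half to two-thirds of the two-sided ones. For independent tests: 14.1/26.5 = 0.53, 26.2/46.0 = 0.57, 53.2/78.5 = 0.68.

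**Period 2.** Only patients with about a 35% irritability improvement at Week 14 continue, so the last row is a simplification. A simulation applied that entry rule under no change, assuming baseline mean 15 or 20, SD 8, retest correlation 0.6 or 0.8 and score correlation 0.3–0.7. On average only 1.5–4 of 20 patients entered Period 2. Over all 30 tests, at least one p<0.05 occurred in 38–72% of trials, or 23–55% counting improvement only. The improvement share then rises to as much as 0.81, because those who continue were selected for improving.

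**Overstatement at Week 14.** The standard error of a mean change is 1/√20 = 0.224 SD of change. The expected maximum of six independent standard normals is 1.27. With common correlation r between scores and the same true effect in all six, the largest observed mean change exceeds the truth by 1.27 × √(1 − r) × 0.224:
- r = 0: 0.28 SD
- r = 0.3: 0.24 SD
- r = 0.5: 0.20 SD
- r = 0.7: 0.16 SD (0.155 before rounding)

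As an illustration, a true 0.3 SD would be reported as about 0.46 SD (r = 0.7) to 0.54 SD (r = 0.3). Sample size scales with 1/effect², so a trial sized on that figure would have (0.3/0.536)² = 31% to (0.3/0.456)² = 43% of the patients needed.

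**Text against text.** The contradictions need no simulation. SAP 6.7 adds efficacy to a primary objective that SAP 3.1 and Protocol 6.1 confine to safety and tolerability. SAP 6.7.1 and 6.7.2 add tests absent from Protocol 13.3 and 13.5, while SAP 10 reports no change.

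**The case against.** The study is openly exploratory (Protocol 13.1, SAP 4.2.1 and 6.7), makes no confirmatory claim and sets no significance level. SAP 3.1 states the formal primary objective correctly. SAP 11 lists change tables for ABC-C, ADAMS, CGI-S and PARS-R, all marked for the Period 1 display, so the other scales will not disappear from view.

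Much of this stands, and it rules out three stronger readings:

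- A reader might infer that the efficacy result is picked after 30 t-tests, so that a false finding arises in half to three-quarters of trials. The SAP's first step is Week 14, with six tests. The 30-test range extends below half, counts significant worsening, and includes 18 tests in a selected subset.
- A reader might infer that the SAP selects the smallest p-value or the largest change and always returns a positive answer. It says neither. Its term is undefined, which is a gap and not a documented rule. The 0.15–0.28 SD applies only if the largest change is the one reported.
- A reader might infer that the primary objective was formally changed. SAP 3.1 shows that it was not; SAP 6.7 contradicts it.

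The exploratory label does not settle the matter. The sponsor's earlier open-label Fragile X study, also with 20 patients enrolled, named a primary endpoint, and Protocol 5.3.2 reports its change-from-baseline p-value as evidence of improvement. SAP 11 ensures that the scores are tabulated, but it does not stop one of them being presented as the efficacy finding.

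**Conclusion.** The point holds in limited form. The conflict over the primary objective, the undefined selection term, the missing criterion for no effect and the omission in SAP 10 all rest on the text alone.

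The error rates are about 16–27% at the SAP's first step, about 25–45% over Period 1 and roughly 35–78% over all 30 tests, with improvement-only figures about half to two-thirds of these (more under responder-only entry to Period 2). They depend on an assumed two-sided 0.05, no true change and assumed correlations. The overstatement of 0.15–0.28 SD of change depends on the largest of six Week 14 changes being reported. None of these figures includes regression to the mean or open-label rating drift, which a single-arm test against 0 cannot separate from a drug effect.

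The documents do not establish that any one score must lead, or that a formal adjustment such as Holm is required in an exploratory study. Irritability might seem the natural lead, but it is caregiver-rated and its Week 14 value decides entry to Period 2. Safety remains the formal primary objective, so this should be corrected but does not undermine the study's main purpose.

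**What to change.** 1. Delete the efficacy phrase from the primary objective in SAP 6.7, so that it matches SAP 3.1 and Protocol 6.1.
2. Present all Week 14 changes together as the efficacy result, whatever their direction: five ABC-C subscales, CGI-S, ADAMS total and five subscales, and PARS-R (13 scores), each with a 95% CI, plus CGI-I.
3. Either name one lead Week 14 score before the data are seen, or state that no single score may be reported as the efficacy finding. The choice is the sponsor's, noting that Irritability also gates Period 2.
4. Label p-values as nominal. Label anything selected after the Period 1 results as hypothesis-generating, not to be used unadjusted to size a later trial.
5. Give no t-test p-values for Weeks 22–38, where only responders remain.
6. List the added t-tests in SAP 10.

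SAP 5.1 planned the Period 1 lock for 06 June 2022, and the Note to File effective 16 February 2026 says that the protocol and SAP will not be updated. If the lock has passed, a lead score can no longer be named in advance; apply the reporting and labelling parts in the study report.

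The cost is a paragraph of text and some table footnotes, with no new data. The downside is fewer nominally significant p-values to quote. If one score is named in advance, 20 patients with data give 80% power at two-sided 0.05 for a mean change of 0.66 SD of change.
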